5.2 Exclusion criteria

1. Recipients of a dual simultaneous kidney/liver, kidney/heart, kidney/lung, or kidney/pancreas transplant
2. History of hypersensitivity to any of the study drugs or to drugs of similar chemical classes
3. Patients being treated with drugs that are strong inducers or inhibitors of cytochrome P450 3A4
4. Patients with a clinically significant systemic infection within 30 days prior to transplant
5. Patients who have any surgical or medical condition that may affect absorption of drug, such as severe diarrhea, active peptic ulcer disease, or uncontrolled diabetes mellitus, which in the opinion of the investigator, might significantly alter the absorption, distribution, metabolism and/or excretion of study medication
6. Women of childbearing potential who are either pregnant, lactating, planning to become pregnant during this trial, or with a positive serum or urine pregnancy test. Women of childbearing potential must be willing to agree to contraceptive practices.
7. Patients who are PCR positive for Hep B, Hep C, or HIV.

6 Treatment

6.1 Investigational drugs

This is a pilot study. All patients will receive tacrolimus extended-release adjusted to target trough levels, mycophenolate mofetil or mycophenolate sodium, and prednisone per CSMC practice. Tacrolimus extended-release will be supplied by Astellas with packs of open-label study drug. A prescription will be filled by the subject for all other drugs.

6.1.1 Patient numbering

Each patient is uniquely identified in the study by a unique subject ID. Upon signing the informed consent form, the patient is assigned a subject ID by the investigator. Once assigned to a patient, a patient number will not be reused.

6.1.2 Dispensing the study drug

Tacrolimus extended-release will be provided free of charge for the duration of the study. Study drug will only be provided up to 12 months post transplant which is the duration of the study. All subjects will be given a prescription for all other drugs to be filled at a local pharmacy after completion of the study.

6.1.3 Study drug supply, storage and tracking

Study drugs must be received by a designated person at the study site, handled and stored safely and properly, and kept in a secured location to which only the investigator and designated assistants have access. Upon receipt, all study drugs should be stored according to the instructions specified on the drug labels. Clinical supplies are to be dispensed only in accordance with the protocol.

6.1.4 Instructions for prescribing and taking the study drug

Medication labels will comply with the legal requirements. The investigator must maintain an accurate record of the shipment and dispensing of study drug in a drug accountability ledger. Patients will be asked to return all unused study drug and packaging at the end of the study or at the time of study drug discontinuation.

The investigator should instruct the patient to take the study drug exactly as prescribed. All dosages prescribed to the patient and all dose changes during the study must be recorded on the Study Drug Administration Record CRF. Depending on when the subject gets transplanted, the investigational drug will either be given same day as transplant (Day 0) OR at the next scheduled dosing after transplantation at 8am. It will be taken by mouth at the starting dose of 5mg orally or 0.07mg/kg (rounded to the nearest 1mg) daily. A therapeutic drug level will be checked after two doses of the investigational drug and then daily as per SOC. Tacrolimus trough levels will be adjusted to achieve a goal of 7 to 9 ng/ml for the first six months and goal of 5-8ng/ml thereafter (see Table 1).

The investigator and co-investigators are responsible for instructing the patients regarding the exact dose and dosing schedule to be followed. Instructions for taking

the drug will be given at the time of discharge and reinforced at subsequent office visits. Patients will be instructed to take the drug at 8am. They will be instructed to take the drug 2 hours after their last meal or 1 hour before their next meal preferably on an empty stomach and to swallow capsules whole (no crushing or chewing or dividing capsules).

Study Drugs

Patients will take tacrolimus extended-release daily on a consistent schedule with regard to time of day and relation to meals. No grapefruit or grapefruit juice should be taken throughout the study.

6.1.5 Permitted study drug dose adjustments and interruptions

Blood for tacrolimus extended-release trough levels will be obtained from all patients at the time points indicated in Flowchart of Procedures. Therapeutic drug monitoring will be mandatory for all patients throughout the study. For patients who are unable to tolerate the protocol-specified dosing scheme, dose adjustments and interruptions are permitted in order to keep the patient on study drug. PI will follow local practice guidelines for these adjustments and interruptions.

The first tacrolimus level should be drawn after two doses are administered. Tacrolimus extended-release dose adjustments should be made based on results of the trough levels from the local laboratory. Follow-up tacrolimus trough levels should be rechecked after any dose adjustments are made to ensure that the recommended troughs are achieved.

6.1.6 Treatment of Acute Rejection

Rejection episodes will be managed as per local practice. Solumedrol or anti-thymocyte globulin will be administered for cell-mediated rejection. IVIG with or without rituximab may be administered for antibody mediated rejection. Plasma exchange +/- eculizumab may be used for severe antibody mediated rejection.

6.1.7 Treatment of patients unable to tolerate oral medication

The study drug may be temporarily interrupted if a patient develops a short-term intolerance of oral medication after the initial dose of study medication. Alternatively, administration of tacrolimus twice daily suspension via nasogastric (NG) tube or if more serious cyclosporine or tacrolimus IV (per SOC) may be used. IV cyclosporine will be preferred due to difficulty checking IV tacrolimus levels (since it is a continuous infusion). Patients should be returned to tacrolimus extended-release oral medication as soon as possible.

7 Visit schedule and assessments

Table 7-1 lists all of the assessments and indicates with an "x" or "SOC" (for standard of care) the visits when they are performed. Patients should be encouraged to attend all visits on the designated day. However, visit windows will be allowed of \pm 1 day for Day 2, \pm 2 days for Day 4, \pm 3 days for

Day 7, Day 14, \pm 7 days for Day 30, Month 2 and \pm 14 days for Month 6, 9, 12.

Table 2 Assessment Schedule

Study Visit	Pre-op	Days							Month			
		Tx Day 0	2 \pm 1d	4 \pm 2 d	7 \pm 3d	14 \pm 3 d	30 \pm 3d	2 \pm 3d	6 \pm 7d	9 \pm 14d	12 \pm 14d	
Informed Consent	X											
Inclusion/Exclusion	X											
Physical Exam	SOC	SOC	SOC	SOC	SOC	SOC	SOC	SOC	SOC	SOC	SOC	SOC
Chest X-ray/ EKG ⁵	SOC											
Transplant Serology / Donor Background	SOC											
Alemtuzumab Administration		SOC										
Safety Lab Tests ¹	SOC	SOC	SOC	SOC	SOC	SOC	SOC	SOC	SOC	SOC	SOC	SOC
Urine Tests ²				SOC	SOC	SOC	SOC	SOC	SOC	SOC	SOC	SOC
Tacrolimus extended-release Trough Level ³			SOC	SOC	SOC	SOC	SOC	SOC	SOC	SOC	SOC	SOC
Viral Testing ⁴							SOC	SOC	SOC	SOC	SOC	SOC
Serum Pregnancy Test ⁶	X											
DSA*	SOC						SOC	SOC	SOC	SOC	SOC	SOC
Adverse Events		X	X	X	X	X	X	X	X	X	X	X

1. CBC and complete metabolic panel

2. Urinalysis

3. Tacrolimus extended-release levels will be monitored 4 days after a dose change or stopping of fluconazole

4. Blood test for: BKV, CMV

* DSA will be done at time of transplant, and quarterly for the first year.

-For DD (diseased donor), sample will be drawn pre-op, prior to IVIG. Majority of patients would have received desensitization within the past 6-9 months prior to transplant.

-For LD, sample will be drawn prior to IVIG-2, but patient would already have received IVIG-1 and ritux 5 weeks prior to sample drawn.

5. Can be done within 6 months of screening date.

6. If subject is of childbearing age. [Not required if subject has a history of hysterectomy].

7.1 Patient demographics/other baseline characteristics

After informed consent has been signed and the patient's eligibility to participate in the study has been determined, baseline patient information will be obtained, such as date of birth, age, sex, race, full relevant medical history/current medical conditions, information on renal transplantation background of recipient and donor and on transplantation procedure. Results of a full physical examination at baseline, vital signs, blood chemistry and hematology, and serum creatinine.

7.2 Treatment exposure and compliance

All doses of study medication administered during the course of the study will be

recorded on the appropriate Study Drug Dosage Administration CRF. Compliance monitoring will be done during clinic visits via patients' interview and drug levels.

7.3 Safety

7.3.1 Acute Rejection

Renal biopsies will be collected for all cases of suspected acute rejection. Biopsies will be read by the local pathologist according to the Banff 2013 criteria. The results will be used for patient management for acute rejection and for the safety analysis.

7.3.2 Graft Loss

The allograft will be presumed to be lost if the patient requires dialysis for three consecutive months or longer and is not able to subsequently be removed from dialysis. If the patient undergoes a graft nephrectomy, then the day of nephrectomy is the day of graft loss. Graft loss is considered a Serious Adverse Event and should be reported on the Serious Adverse Event CRF and the SAE form.

7.3.3 Death

In the event of patient death, an SAE form should be completed and reported. The events leading to the death should be entered on the Adverse Event CRF.

7.3.4 Renal function

Renal function will be assessed by measuring serum creatinine and by calculated GFR using the MDRD formula.

7.3.5 Viral PCR

CMV and BKV PCRs will be collected according to the schedule outlined in Table 2.

7.4 Physical examination

A thorough physical examination will be performed during the baseline period and at every subsequent study visit. Significant findings made after the start of study drug which meet the definition of an Adverse Event will be recorded on the Adverse Event monitoring log.

7.4.1 Vital signs

Vital signs (pulse rate, blood pressure and weight (to the nearest 0.1 kilogram [kg]) will be recorded at baseline, prior to the first morning administration of study medication, and at each subsequent visit.

7.4.2 Laboratory evaluations

A local laboratory (Cedars-Sinai Clinical Reference Laboratory) will be used to analyze the clinical laboratory data during the study.

Hematology

Hematology will include platelets, hemoglobin, red blood cell count, white blood cell count to be measured at every study visit.

Clinical chemistry

Biochemistry parameters will include sodium, potassium, chloride, calcium, magnesium, inorganic phosphate, blood urea nitrogen, creatinine, glucose, AST, ALT, alkaline phosphatase, total bilirubin.

Urinalysis

Measurements will be taken for cell count, glucose, and protein.

7.4.3 Pregnancy and assessments of fertility

Any female patient that becomes pregnant after the start of study medication should be discontinued and the patient switched to standard treatment. All pre-menopausal women who are not surgically sterile will have a serum pregnancy test at screening and a urine pregnancy test, if suspected, and at the end of study visit. A positive urine pregnancy test requires immediate interruption of study medication until serum B-hCG is performed and found to be negative. If positive, the patient must be discontinued from the trial. The pregnancy should be followed up to determine outcome, including spontaneous or voluntary termination, details of birth, and the presence or absence of any birth defects or congenital abnormalities.

8 Safety monitoring

8.1 Adverse events

An adverse event is the appearance or worsening of any undesirable sign, symptom, or medical condition occurring after starting the study drug even if the event is not considered to be related to study drug. Study drug includes the investigational drug under evaluation. Medical conditions/diseases present before starting study drug are only considered adverse events if they worsen after starting study drug. Abnormal laboratory values or test results constitute adverse events only if they induce clinical signs or symptoms, are considered clinically significant, or require therapy. The occurrence of adverse events should be sought by non-directive questioning of the patient at each visit during the study. Adverse events also may be detected when they are volunteered by the patient during or between visits or through physical examination, laboratory test, or other assessments.

8.2 Serious adverse event reporting

An SAE is defined as an event which:

- is fatal or life-threatening
- results in persistent or significant disability/incapacity
- constitutes a congenital anomaly/birth defect
- requires inpatient hospitalization greater than 24 hours unless hospitalization is for:
 1. routine treatment or monitoring of the studied indication, not associated with any deterioration in condition
 2. elective or pre-planned treatment for a pre-existing condition that is unrelated to the indication under study and has not worsened since the start of study drug
 3. treatment on an emergency outpatient basis for an event not fulfilling any of the definitions of a SAE given above and not resulting in hospital admission
 4. social reasons and respite care in the absence of any deterioration in the patient's

general condition is medically significant, i.e. defined as an event that jeopardizes the patient or may require medical or surgical intervention to prevent one of the outcomes listed above.

All SAEs that are **serious** and **reasonably or probably related** to tacrolimus extended-release will be reported to FDA and Astellas Pharma using MedWatch 3500A form (Appendix B).

Recurrent episodes, complications, or progression of the initial SAE must be reported as follow-up to the original episode, regardless of when the event occurs. An SAE that is considered completely unrelated to a previously reported one should be reported separately as a new event.

All SAEs will be reported to Astellas. Their contact information is listed below:

Email: [contact].

[contact]

Protocol exempted events: Unusually severe rejection episodes

Acute rejections are considered protocol exempted events. They should not be reported simply because they result in hospitalization thus meeting the criteria for SAEs. Acute rejection episodes will therefore not be routinely expedited to health authorities. However, acute rejections should be reported as SAEs if they are unusual in appearance, clinical course and/or are graft threatening.

8.3 Pregnancies

To ensure patient safety, each pregnancy in a patient on study drug must be reported within 24 hours of learning of its occurrence. The pregnancy should be followed up to determine outcome, including spontaneous or voluntary termination, details of the birth, and the presence or absence of any birth defects, congenital abnormalities, or maternal and/or newborn complications.

9 Data review and database management

9.1 Data collection

Designated research staff will enter data into a secure electronic database from source documents. Only the PI and designated research staff will have access to the database. All source documents will be kept in a secure, locked cabinet. All data will be reviewed for accuracy. Designated research staff will be trained in the use of the electronic database.

If patients live far from CSMC and are unable to come to their designated study visits within study windows, the study team will try to obtain study labs from the patient's local hospital/clinic. The results will be forwarded to CSMC for analysis.

9.2 Database management and quality control

Designated study staff will validate data on an ongoing basis. Any errors noted will be reviewed, confirmed, and then corrected. A statement noting the correction will be included. This study will be monitored by a formal DSMB. The DSMB will consist of the PI, appointed Co-PIs, and at least one member not part of the investigational group. The DSMB will review safety data quarterly and formulate a letter with recommendations for continuation.

10 Data analysis

A designated statistician will perform the statistical analysis.

10.1 Populations for analysis

All patients enrolled in the study will be included in the analysis.

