Appendix

Appendix 1:	Data Safety Monitoring Board (DSMB) Charter.....	21
Appendix 2:	MedWatch Form.....	21
Appendix 3:	Tacrolimus Extended Release (Astagraf XL®) Package Insert.....	21

List of tables

Table 1	Target Tacrolimus Extended Release Trough Levels.....	8
Table 2	Assessment Schedule.....	14

List of abbreviations

HS	Highly Sensitized
IVIG	Intravenous Immunoglobulin
PLEX	Plasma Exchange
SAEs	Serious Adverse Events
BPAR	Biopsy proven acute rejection
DSA	Donor Specific Antibodies
PRA	Panel reactive antibody
CSMC	Cedars-Sinai Medical Center
TMP/SMX	Trimethoprim/Sulfamethoxazole (Bactrim)
HLA	Human Leukocyte Antigen Antibodies
RIS	Relative Intensity Score
MFI	Mean Fluorescence Intensity
CRF	Case Report Form
SOC	Standard of Care
SAE	Significant Adverse Event
FDA	Federal Drug Administration
WHO	World Health Organization

Glossary of terms (correct format below)

Assessment	A procedure used to generate data required by the study
Control drug	A study drug used as a comparator to reduce assessment bias, preserve blinding of investigational drug, assess internal study validity, and/or evaluate comparative effects of the investigational drug
Enrollment	Point/time of patient entry into the study; the point at which informed consent must be obtained (i.e. prior to starting any of the procedures described in the protocol)
Investigational drug	The study drug whose properties are being tested in the study; this definition is consistent with US CFR 21 Section 312.3 and is synonymous with “investigational new drug.”
Medication number	A unique identifier on the label of each medication package in studies that dispense medication using an IVR system
Patient number	A number assigned to each patient who enrolls in the study. When combined with the center number, a unique identifier is created for each patient in the study.
Stage	A major subdivision of the study timeline; begins and ends with major study milestones such as enrollment, randomization, completion of treatment, etc.
Period	A minor subdivision of the study timeline; divides phases into smaller functional segments such as screening, baseline, titration, washout, etc.
Premature patient withdrawal	Point/time when the patient exits from the study prior to the planned completion of all study drug administration and assessments; at this time all study drug administration is discontinued and no further assessments are planned

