Randomization number	A unique identifier assigned to each randomized patient, corresponding to a specific treatment arm assignment
Stop study participation	Point/time at which the patient came in for a final evaluation visit or when study drug was discontinued whichever is later
Study drug	Any drug administered to the patient as part of the required study procedures; includes investigational drug and any control drugs
Study drug discontinuation	Point/time when patient permanently stops taking study drug for any reason; may or may not also be the point/time of premature patient withdrawal
Variable	Information used in the data analysis; derived directly or indirectly from data collected using specified assessments at specified timepoints

Protocol synopsis

Title of study: A Prospective, Pilot Trial to Evaluate the Safety and Tolerability of Tacrolimus Extended-Release in HLA Sensitized Kidney Transplant Recipients

Purpose and rationale:

The purpose of this study is to demonstrate the safety of tacrolimus extended-release in HLA sensitized (HS, defined as panel reactive antibody $\geq 30\%$), kidney transplant recipients after desensitization with intravenous immunoglobulin (IVIG) and rituximab +/- plasma exchange (PLEX) per the standard of care with alemtuzumab induction.

Objectives:

The primary objective is to determine the safety of tacrolimus extended-release in the HS patient population as measured by the rate of serious adverse events (SAEs) and treatment failure. Treatment failure is defined as a composite of biopsy proven acute rejection (BPAR), graft failure, or death. BPAR is defined as \geq Banff 1A using the Banff 2007 criteria.

Secondary objectives are to observe the following:

1. Change in donor specific antibodies (DSA) as defined by the DSA relative intensity score[1,2]
2. Tolerability as defined by the number of subjects discontinuing the study medication

Population:

The study population will consist of HS patients (patients who have received desensitization) with end- stage kidney disease undergoing kidney transplantation. The study will begin at the time of transplantation while subjects are inpatients. They will be followed post- transplantation as outpatients.

Inclusion/Exclusion criteria:

Key **inclusion criteria** are as follows:

1. Recipient of a deceased or living donor kidney allograft

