Tacrolimus trough level, complete metabolic panel, liver function panel, complete blood count with differential, DSA, and urinalysis with culture will be assessed according to the evaluation schedule below. Subjects will complete the study at one year post-transplant. Consent may be withdrawn by the study participant at any time. The investigator may also withdraw the study participant at any time if there are any safety concerns.

Desensitization includes Intravenous Immunoglobulin (IVIG) 2g/kg (>70kg max 140g) given on day 0 (split over 2 days for peritoneal dialysis patients), rituximab 375mg/m² (rounded to the nearest 100mg vial) given on day 15, and IVIG 2g/kg (>70kg max 140g) given on day 30. Patients will require plasma exchange (PLEX) 5-7 sessions if they have received desensitization in the past. In this case, patients will receive PLEX daily x 5-7 sessions followed by IVIG 2g/kg (>70kg max 140g) and rituximab 375mg/m². Patients will be receiving acetaminophen, antihistamine, and steroid as premedication for all infusions.

5 Population

Male and female HS renal transplantation patients, 18 years of age and over, receiving a cadaveric or living donor kidney transplant may enter the study. Patients must

receive desensitization therapy. Twenty patients will be enrolled at CSMC for this pilot study. Patients who discontinue the study prematurely will not be replaced.

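### One-year treatment failure is reported over all enrolled patients, but follow-up stops at premature withdrawal, late dialysis-based graft loss has no date, and unknown status has no rule

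*Combined protocol and SAP*

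**What the plan says.** - **Analysis set (10.1):** "All patients enrolled in the study will be included in the analysis". Twenty patients are planned (10.5). Section 5 adds: "Patients who discontinue the study prematurely will not be replaced".
- **Variable (10.4.1):** treatment failure at one year, a composite of BPAR, graft failure or death, summarised as a frequency and percentage. The synopsis places the SAE rate beside it in the primary objective.
- **Premature withdrawal (glossary):** "at this time all study drug administration is discontinued and no further assessments are planned".
- **Drug discontinuation (glossary):** a separate event, which "may or may not also be the point/time of premature patient withdrawal".
- **Who may withdraw a patient (section 4):** the patient may withdraw consent, and "The investigator may also withdraw the study participant at any time if there are any safety concerns".
- **Graft loss (7.3.2):** presumed if the patient "requires dialysis for three consecutive months or longer and is not able to subsequently be removed from dialysis". A date of loss is given only for graft nephrectomy.
- **End of participation (synopsis, section 4):** one year post-transplant. The month-12 window is ±14 days (section 7).
- **SAE follow-up (8.2):** "Recurrent episodes, complications, or progression of the initial SAE must be reported as follow-up to the original episode, regardless of when the event occurs".

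Sections 10.1 and 10.4 say nothing about a patient whose one-year status is unknown. The only related rule, in 10.3, sets doses to zero during interruptions and concerns average dose.

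**The concern.** To count someone as a non-failure at one year, the analyst must know that no rejection, graft loss or death occurred up to then. The withdrawal definition ends planned data collection before that can be known. One route into withdrawal is a safety concern, so the patients lost may be those at higher risk. Failures before withdrawal are counted; those afterwards may not be.

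The consequence depends on an unstated choice. If patients withdrawn event-free are counted as non-failures, the rate can only be understated. If they are dropped from the denominator, it can err either way, and 10.1 is no longer followed.

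The graft-loss rule raises a smaller question of the same kind. It needs three months of observation and then an open-ended look forward, while participation ends at one year. Two analysts could classify the same late-dialysis patient differently and both claim to follow the text.

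**Working it through.** The plan derives no figure for this endpoint, so there is nothing to reproduce. The checks below bound the effect.

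**Inputs from the documents:** N = 20; all enrolled analysed; no replacement; one-year endpoint; month-12 window ±14 days; three-month dialysis rule. **Assumed, because the documents are silent:** number of observed failures f, number of unknown outcomes w, probability d that a patient's status is unknown, yearly incidence p of lasting dialysis, and three months taken as 91 days.

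**1. Weight of one patient.** 1/20 = 5 percentage points.

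**2. Range from unknown outcomes.** The lowest rate is f/20 and the highest is (f + w)/20, so the width is w/20: 5, 10, 15 or 20 points for w = 1, 2, 3 or 4, whatever f is. Dropping unknowns gives f/(20 − w). With an assumed f = 4 and exact (Clopper-Pearson) 95% intervals:

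| w | Unknown = non-failure | Unknown dropped | Unknown = failure |
|---|---|---|---|
| 1 | 4/20 = 20.0% (5.7–43.7) | 4/19 = 21.1% (6.1–45.6) | 5/20 = 25.0% (8.7–49.1) |
| 2 | 20.0% (5.7–43.7) | 4/18 = 22.2% (6.4–47.6) | 6/20 = 30.0% (11.9–54.3) |
| 3 | 20.0% (5.7–43.7) | 4/17 = 23.5% (6.8–49.9) | 7/20 = 35.0% (15.4–59.2) |
| 4 | 20.0% (5.7–43.7) | 4/16 = 25.0% (7.3–52.4) | 8/20 = 40.0% (19.1–63.9) |

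**3. Chance of at least one unknown.** 1 − (1 − d)^20 gives 33%, 64%, 88% and 96% for d = 2%, 5%, 10% and 15%.

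**4. Dialysis dates.** The latest start that can complete 91 days is 365 − 91 = day 274. With the visit at day 351 it is 351 − 91 = day 260; at day 379 it is 379 − 91 = day 288. For a start on days 275–365 that persists, dating loss to the first dialysis day makes the patient a one-year failure, while dating it to completion of three months puts the loss outside the endpoint. That is 91 of 365 days, or 24.9% of calendar time (not of graft losses). In the other direction, a graft presumed lost at month 12 may later prove not to be, since the second condition has no time limit.

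**5. How often the dialysis question might arise.** With uniform onset, the expected number is 20 × p × 91/365 = 0.10, 0.25 or 0.50 patients for p = 2%, 5% or 10%. The chance of at least one is 1 − (1 − p × 91/365)^20 = 9.5%, 22.2% or 39.6%. These are upper figures for each p, because patients already failed through BPAR, nephrectomy or death are not removed.

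Steps 4 and 5 take graft failure in 10.4.1 to mean graft loss in 7.3.2. The synopsis supports this by listing graft loss with BPAR and death, but does not state it.

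**The case against.** The strongest reply is that this is a 20-patient descriptive pilot. It has no margin, test or decision rule for a 5-point shift to cross, and all outcomes are reported as frequencies. That limits the severity and stands. It does not settle how the reported percentage is formed.

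A second reply is that section 8.2 already supplies the follow-up, since progression of an SAE is reported whenever it happens. Dialysis starting before month 12 would probably qualify as an SAE, so the later course may well be on record. This stands for the data, but 8.2 gives neither a date of loss nor a classification. For withdrawn patients it reaches only SAEs already reported. It also exempts ordinary acute rejection from SAE reporting, so it helps least with BPAR. Section 9.1 allows local laboratory results for patients living far away; it does not address withdrawn patients, biopsies, graft status or vital status.

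Three stronger readings are tempting and should not be drawn:

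- A reader might infer from the glossary entry on stopping participation ("Point/time at which the patient came in for a final evaluation visit or when study drug was discontinued whichever is later") that follow-up ends when drug stops. The synopsis and section 4 keep subjects in the study to one year, and the glossary separates drug discontinuation from withdrawal. The gap concerns withdrawal only.
- A reader might call the failure proportion the trial's sole main result. The SAE rate is also part of the primary objective.
- A reader might conclude that the analysis set must be redefined. The sentence in 10.1 is not itself wrong; what is missing is outcome collection and a classification rule.

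**Conclusion.** The concern holds in limited form. As written, the plan can leave one-year treatment failure unknown for patients withdrawn event-free, possibly for reasons related to outcome, and it has no rule for them. Each such patient widens the possible rate by 5 points. This is arithmetic on N = 20 and needs no assumed event rate.

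The late-dialysis gap is real but smaller. It is confined to starts after about day 274 (day 260 to 288 across the visit window) in patients not already counted through another component. What is missing there is a date and a classification, and not necessarily the data.

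The size and direction of any actual bias cannot be derived. The failure count, the probabilities of unknown status and the dialysis incidences above are illustrations only. Severity is minor to moderate, and the gaps are cheap to close.

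**What to change.** 1. **Glossary and section 4:** after drug discontinuation or investigator withdrawal, keep collecting biopsy results, graft status and vital status from the clinic record to month 12, unless consent is withdrawn.
2. **Sections 7.3.2 and 10.4.1:** use one term for graft loss and graft failure. For endpoint classification only, date dialysis-based loss to the first day of the continuous dialysis period. For anyone on dialysis at month 12, confirm status from the record about three months later.
3. **Section 10.4.1:** name one primary rule for any one-year status still unknown, for example observed failures over all enrolled patients with the number unknown shown. That choice is the lower bound, so report best- and worst-case bounds beside it.

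The cost is amendment wording, a few chart look-ups, and up to about 91 days' wait for final graft status if anyone is on dialysis at month 12. The reported rate may be less favourable. Patients who withdraw consent may still have unknown outcomes, which is why item 3 is needed as well as item 1. No treatment, visit or sample size changes.
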